Cover page for clinical trials.gov

Official Study Title: Socio-Structural Intervention to Improve Pre-Exposure Prophylaxis Services for Cisgender Women (PrEP CGW)

NCT number: pending

Date of Document: May 3, 2021

STATISTICAL DESIGN & POWER

Aim 1: Intervention Development. We will recruit n=10 key informants for in-depth interviews and up to n=60 CGW and medical providers to contribute to the focus groups (2-3 groups per population with groups of 8-10 participants) and theater testing.

Aim 2: Feasibility Trial. Given the pilot nature of this study, it is not appropriate to conduct a power analysis; We are not testing effectiveness during this stage of the trial.¹

Measures & Analysis. Data collection will be ongoing in through the EMR; reach and initial effects data will be extracted for all CGW at three time points (baseline, intervention, and discontinuation). More detailed data in regard to the intervention strategies (provider training and peer navigation) will be collected on Adoption and Implementation (feasibility and acceptability) at the end of the intervention time period as described in **Table 1** below.

Table 1. Aim 2 Outcomes, Data Sources, and Time Points for Evaluation

Outcome	Data Source/ Measure	Time of Evaluation*
Reach (also shows feasibility of intervention)		
% of eligible CGW counseled on PrEP by providers	EMR	Year 3, Quarter 2 (End of Intervention)
% of CGW who complete HIV prevention discussion with peer navigator	Comparison of peers' patient log with EMR patient visit log	Year 3, Quarter 2
Measure of Initial Effects (note: no statistical testing for effectiveness in pilot phase; measures are for feasibility of data collection and standard deviation calculation)		
% change in perceived medical bias	7-item Discrimination in Medical Settings Scale	Year 2, Quarter 3 & Year 3 Quarters 1&2
% eligible CGW initiate PrEP	EMR	Year 3, Quarter 2
Of CGW who initiate PrEP, % adherence at 1 month	EMR, DBS**, & Pharmacy Data	Year 3, Quarter 2
Of CGW who initiate PrEP, >75% will persist \geq 1 month	EMR & Pharmacy Data	Year 3, Quarter 2
Adoption		
% of providers who participate in synchronous or asynchronous training	Attendance log	Year 3, Quarter 2
% change in knowledge/awareness of medical bias and positive PrEP counseling techniques	Provider training module pre- & post-knowledge questionnaires	Year 2 Quarter 4- Year 3 Quarter 1
Implementation		
Perceived feasibility of implementing the intervention	Provider & Peer Likert scale survey & Provider & Peer in-depth interviews (n=10)	Year 3, Quarter 2
Acceptability: % CGW who receive provider counseling or peer session and report high satisfaction	CGW; Likert scale survey to rate affective attitude, or feelings towards the intervention, burden, or perceived amount of effort to participate, and congruence with individual values ²	Year 3, Quarters 1-2 (Post-clinical visit or peer session)
Satisfaction with training (synchronous vs. asynchronous) and outreach intervention among providers and peers	Provider & Peer Likert scale survey; Provider & Peer in-depth interviews (n=10)	Year 2 Quarter 4 - Year 3 Quarter 2 (Beginning, mid, & end of intervention) Year 3, Quarters 1-2
Organizational perspective on the intervention	Provider & Peer in-depth interviews (n=10)	Year 3, Quarters 1-2
Patient perspective on the intervention	Patient in-depth interviews (n=20)	Year 3, Quarters 1-2

*See **Study Timeline** in PHS

For percentage outcomes we will use the following “traffic light” benchmark system for feasibility and acceptability in Aim 2: 0-50%: failure of the current intervention design; 51-75%: major revisions required; 76%: no or minor revisions needed for a confirmatory trial.

Questionnaires. RAs will invite all CGW seen in FPPC to participate in a 5-minute tablet-based survey to assess acceptability of the provider and peer components of the intervention and intention to initiate PrEP; CGW seen virtually will be contacted by phone and/or email and invited to participate in an online survey. We anticipate that approximately 300 CGW will complete the survey. Upon survey completion, participants will be invited to provide their contact information to participate in virtual or in-person IDI. Additionally, to assess intermediate effects of the provider trainings, we plan to use the 7-item Discrimination in Medical Settings Scale³, which has been validated in Black populations, to capture changes in patient-reported experiences before and after implementation of trainings to capture participant perceptions of bias.

Adoption by providers will be measured using attendance logs, with the goal of >75% of providers completing trainings. Additionally, we will evaluate the educational impact of the provider trainings with pre- & post-knowledge questionnaires for all training participants. **Implementation** outcomes focus on feasibility and acceptability, which will be evaluated both quantitatively and qualitatively. For quantitative measures we will use a validated, 8-item Likert scale to be completed by providers and peer navigators.⁴ We will also use the Theoretical Framework for Acceptability, with seven domains on a Likert scale to assess ethicality, affective attitude, experienced burden, opportunity costs, perceived effectiveness, self-efficacy, and intervention coherence.²

Feasibility and Acceptability will also be assessed in qualitative, in-depth interviews with patients and providers. Transcripts will be uploaded into the qualitative data analysis software, *Atlas.ti*,^{5,6} for the purposes of coding and analysis. We will first develop an *a priori* code book⁶ that reflects key analytic concepts related to topical areas described above contained in the semi-structured interview guide. During the process of reading and coding of transcripts using this initial coding scheme, additional codes may be added to document emerging domains of interest. Qualitative analysis will proceed by first exploring broad patterns of perspectives and experiences. For FGDs, we will look for patterns of consensus and divergence within groups, and comparative perspectives between groups e.g., potential PrEP users and providers in terms of receptiveness for intervention plans for both the provider trainings and peer navigation components. For IDIs, we will assess similarities and differences between types of participants for patients and providers, respectively, (e.g., variation by demographics, level and type of engagement) and then across the groups to gain insight into how the intervention was received and variation in acceptability.

These qualitative and quantitative data will then be triangulated to refine the interventions for the future full-scale trial.

Quantitative data will be entered into REDCap for structured data storage and analyzed using Python/R language. We will conduct a descriptive summary of the outcomes described in the above Table 1. Where appropriate, we will test item scale reliability using the intraclass correlation coefficient (ICC). In surveys we will also collect data on demographics (e.g., race, age, education, income, partner status), behavioral risk for HIV (e.g., number of sexual partners, HIV status of partner, consistency of condom use), medical history (e.g., comorbidities, duration of risky behaviors), and lifestyle habits (e.g., smoking, alcohol consumption, substance abuse). We will also describe the demographic and clinical characteristics of CGW included in the sample, including means (standard deviations) or medians (interquartile ranges), and frequencies (percentages). Following descriptive statistics, we will compare the proportions of CGW who initiate PrEP and persist ≥ 1 month by key characteristics (e.g., age, partner status). We will use logistic regression to explore characteristics of those initiating PrEP and continuing past one month.

In order to better estimate treatment standard deviations, we will explore RDD analyses in preparation for our future effectiveness trial. RDD is a quasi-experimental, pretest-posttest design, it is commonly used for causal research studies, which involve distinct cutoff values that assign subjects into different conditions and compare different conditions' outcomes. In the full-scale effectiveness trial, we will isolate the treatment effect by designing a baseline period (months 6-9 in year 2) and intervention period (month 12 year 1 to month 3, year 3), and will determine the cutoff points before the data collection. The design allows an unbiased estimate of the treatment effect by minimizing confounding bias and assessing the magnitude of the discontinuity on outcomes at the cutoff point. We will also consider potential confounders of demographics factors including age, income, partner status in the analysis to achieve comparability and exchangeability.

Capperlieri et.al. conducted a power analysis using $\alpha = .025$ (one-tailed) and provided recommendations for the sample sizes for detecting different standardized effect sizes.⁷ Their results show: 1) a sample of 1078 would have a power of .80 for detecting a small effect size, 2) a sample of 150 would have a power of .80 for detecting a medium effect size, 3) a sample of 68 would have a power of .80 for detecting a large effect size, and 4) a sample size of 109 would have power of .95 for detecting a large effect size. While we are not conducting effectiveness testing at this stage, our numbers should allow for calculation of standard deviations to prepare for our fully powered trial. Based on their study, we will recruit an adequately sample size of CGW participants for the preliminary RDD analysis (i.e., 460 CGW participants during the intervention period, an additional 345 CGW participants in the baseline, and 460 in the discontinuation period).

[name] will conduct analyses in PythonR⁸. All data reporting will follow the CONsolidated Standards of Reporting Trials (CONSORT) guidelines.⁹

5. ATLAS.ti: The Qualitative Data Analysis & Research Software. Accessed January 7, 2021. <https://atlasti.com/>

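### The perceived-bias outcome is defined as a percent change of a scale score, which depends on item coding and does not suit its stated purpose of estimating a standard deviation

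*SAP*

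**What the plan says.** In SAP Table 1, under Measure of Initial Effects, the first outcome is a percent "change in perceived medical bias". It is measured by the "7-item Discrimination in Medical Settings Scale" in Year 2 Quarter 3 and Year 3 Quarters 1 and 2. The heading of that block rules out effectiveness testing and adds that the "measures are for feasibility of data collection and standard deviation calculation".

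The Questionnaires paragraph says that the scale is used "to capture changes in patient-reported experiences before and after implementation of trainings to capture participant perceptions of bias". It does not say whether the same women answer both times. The paragraph on numbers for the preliminary RDD analysis plans for "460 CGW participants during the intervention period, an additional 345 CGW participants in the baseline", and says that these numbers should yield standard deviations for the fully powered trial.

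The SAP does not give the response options, the item coding, a formula for percent change, or the level (woman or group) at which it is taken. The analysis text promises only a descriptive summary of the Table 1 outcomes.

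A second row of the same form, a percent "change in knowledge/awareness of medical bias and positive PrEP counseling techniques", stands under Adoption. That block carries no note about standard deviations.

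**The concern.** The block exists to supply standard deviations for planning, but its first outcome is expressed in a form that does not supply a usable one. A sum or mean of ordinal items has no natural zero. Dividing a change by the baseline score therefore divides by a number that is partly an artefact of whether the lowest answer is coded 0 or 1.

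Two things are at stake:

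- **The reported figure.** The same answers can appear as a small or a large reduction in perceived bias, depending on a coding choice that the SAP does not state.
- **The planning input.** A percent change is either a single group-level ratio, with no spread between women, or a person-level quantity whose spread moves with the coding. Planners of a later trial need the spread of the score itself, in known units.

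**Working it through.** **Inputs.** From the SAP: seven items, a percent change, and a stated standard-deviation purpose. The SAP gives no mean, standard deviation or effect for this outcome, so there is no figure of its own to reproduce. Assumed here: five response options, coded 1-5 (total 7 to 35) or 0-4 (total 0 to 28), and a mean fall of 0.3 per item, that is 7 × 0.3 = 2.1 points.

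**Step 1: dependence on the origin.** Let T be the baseline total under 1-5 coding. The same answers give T − 7 under 0-4 coding. A fall of d points is 100·d/T percent under the first coding and 100·d/(T − 7) percent under the second, so the two differ by the factor T/(T − 7).

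| Baseline item mean (1-5 coding) | Total, 1-5 | Total, 0-4 | Fall, 1-5 | Fall, 0-4 | Factor |
|---|---|---|---|---|---|
| 2.0 | 14 | 7 | 2.1/14 = 15% | 2.1/7 = 30% | 2 |
| 1.5 | 10.5 | 3.5 | 2.1/10.5 = 20% | 2.1/3.5 = 60% | 3 |

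The factor shrinks as the baseline score rises: at an item mean of 3.0 it is 21/14 = 1.5. Averaging items instead of summing them changes nothing, because numerator and denominator are both divided by 7.

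**Step 2: what standard deviation the outcome yields.**

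- *Different women before and after.* Percent change is (mean after − mean before)/mean before. That is one number. It has a standard error, but there is no between-woman standard deviation of it.
- *The same women, linked.* A percent change exists for each woman with a nonzero baseline, and so does its standard deviation. In simulated paired scores under the assumed coding (baseline mean 4.54 and later mean 3.25 on the 0-28 total), the person-level standard deviation was 18.5 percentage points under 1-5 coding and 68.5 under 0-4 coding. Under 0-4 coding, 26% of women had a baseline of zero and no defined value. The group-level change was −11.1% (−1.285/11.536) under 1-5 coding and −28.3% (−1.285/4.536) under 0-4 coding.

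**Step 3: the same data as points.** Subtracting 7 from every total changes neither a standard deviation nor a difference. In the simulation the baseline standard deviation was 5.19 points and the standardised shift −1.285/5.19 = −0.25 under both codings.

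The simulated values only illustrate the mechanism. They are not estimates for this trial.

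**The case against.** The strongest reply is that nothing is lost. Scores are collected in each period, the SAP plans a descriptive summary, and an analyst can compute a raw-score standard deviation whatever the row is called. That stands. A reader might infer that the pilot cannot deliver a standard deviation at all, and the SAP does not support this. What remains is that the defined outcome is not the quantity that serves the stated purpose.

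Second, the scale is an existing validated instrument, and its coding may be fixed by its source or by a protocol. This is fair, and it makes the 15% versus 30% contrast illustrative. A stated coding would make the figure reproducible, but the percentage would still depend on that coding.

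Third, the row could mean a change in the percentage of women who report bias, which has no origin problem. The SAP does not say so and gives no threshold for counting a woman as reporting bias. The reading is possible and should be confirmed or ruled out.

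Fourth, in the simulation the ratio of person-level mean to standard deviation was nearly the same under both codings: −8.0/18.5 = −0.43 and −30.0/68.5 = −0.44. So a standardised effect need not shift much. But the second figure leaves out the 26% of women with a zero baseline, and neither standard deviation can be used without knowing the coding.

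Fifth, a reader might take the sentence "RAs will invite all CGW seen in FPPC to participate in a 5-minute tablet-based survey" as proof that bias scores come unpaired from whoever attends. That sentence describes the survey of acceptability and intention to start PrEP. The bias scale is introduced afterwards, with no recruitment method given. The better evidence is the wording about additional baseline participants, and it is only suggestive.

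Finally, a reader might extend the point to provider knowledge. The documents do not support that as an error. The standard-deviation note is not attached to Adoption, a number-correct score has a natural zero, and "pre- & post-knowledge questionnaires for all training participants" makes within-provider pairs plausible.

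**Conclusion.** The point holds for perceived medical bias, as a fault in the outcome definition. The block's purpose is to obtain standard deviations, and a percent change of a 7-item scale score either has no between-woman standard deviation (unlinked women) or has one that depends on the coding (linked women). The coding alone changes the reported percentage by a factor of 2 to 3 in the two worked cases. This rests on an assumed five-option format and assumed low baseline means; the factor is smaller at higher baselines.

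The consequence is limited. The SAP plans no effectiveness test, so no error rate or decision is affected. It also does not name perceived bias as an endpoint of the full-scale trial, so a claim that the later trial's planning would fail goes beyond the text. Whether women are linked is open in the document, and the conclusion does not depend on the answer.

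**What to change.** In Table 1, replace the percent change in perceived bias with the mean scale score and its standard deviation in each period, and the difference between periods in points. State the item coding and whether the score is a sum or an item mean. State whether women are linked across periods and, if they are, also report the standard deviation of the within-woman difference. If a change in the percentage of women reporting bias was meant, say so and define the threshold.

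The change uses the same data and alters only SAP wording. The only loss is the percent figure.

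Optional, as a reporting preference: give provider knowledge as the within-provider change in percent-correct points, with its standard deviation. A relative change reads the same 20-point gain as 20/40 = 50% from a start of 40 and 20/80 = 25% from a start of 80.

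### Does the missing scoring rule for high satisfaction, with three acceptability domains in one place and seven in another, undermine the traffic-light grade?

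*SAP*

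**What the plan says.** Table 1, under Implementation, defines the women's outcome as "Acceptability: % CGW who receive provider counseling or peer session and report high satisfaction". The measure in that row is a Likert survey in which women "rate affective attitude, or feelings towards the intervention, burden, or perceived amount of effort to participate, and congruence with individual values", which is three domains. The Questionnaires paragraph describes the vehicle: women are invited to "participate in a 5-minute tablet-based survey to assess acceptability of the provider and peer components of the intervention", with about 300 completions expected.

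The note under Table 1 applies a "benchmark system for feasibility and acceptability in Aim 2" to percentage outcomes, with the bands "0-50%: failure of the current intervention design; 51-75%: major revisions required; 76%: no or minor revisions needed for a confirmatory trial".

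The paragraph on Adoption and Implementation says that these "outcomes focus on feasibility and acceptability, which will be evaluated both quantitatively and qualitatively". It continues: "For quantitative measures we will use a validated, 8-item Likert scale to be completed by providers and peer navigators". The next sentence adds the acceptability framework "with seven domains on a Likert scale to assess ethicality, affective attitude, experienced burden, opportunity costs, perceived effectiveness, self-efficacy, and intervention coherence" and does not say who answers it.

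The quantitative analysis paragraph plans a descriptive summary of the Table 1 outcomes. The quantitative and qualitative results are then to be combined to refine the intervention.

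**The concern.** Two things look wrong.

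1. The same published framework appears with three domains in Table 1 and seven in the text. If both feed the women's percentage, there are two versions of one graded outcome.
2. Satisfaction is not itself one of the listed domains. The SAP gives no item cut-off, no way of combining domains and no scoring direction for burden, where a low score is the favourable one.

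The bands label a design as failed, in need of major revision, or nearly ready for a confirmatory trial. If the meaning of high satisfaction can be settled once the answers are in, a benchmark fixed in advance protects less than it appears to.

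A smaller point of the same kind concerns training. Table 1 counts providers who take part, while the text sets its target of more than 75% on providers who complete.

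**Working it through.** **Do the two places contradict each other?**

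| Place in the SAP | Instrument | Who answers |
|---|---|---|
| Table 1, Acceptability row | three domains, Likert | women receiving counselling or a peer session |
| Implementation text, first scale | 8 items, Likert | providers and peer navigators |
| Implementation text, second scale | seven domains, Likert | not stated |

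Table 1 fixes three domains for the women's row, and nothing in the text overrides that. The seven-domain sentence follows directly on one about staff, and Table 1 has a separate Likert row for satisfaction among providers and peers. A short three-domain survey for women and the fuller set for staff is a consistent reading.

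It might be argued that the women's row is the only one in Table 1 to cite the framework's reference. But it is the only row in Table 1 that cites any numbered reference, so the silence of the staff rows shows nothing.

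**How far could the choice move the percentage?**

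The SAP states no figure for this outcome, so there is none to reproduce. The inputs are:

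- from the SAP: the bands, and about 300 respondents;
- assumed: a share *p* of women agreeing on each domain (80 to 95%), a common latent-normal correlation *ρ* between domains (0.3 to 0.7), and a 5-point scale.

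Sampling yardstick: 1.96 × √(0.75 × 0.25 / 300) = 0.049, or 4.9 points.

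*Strict rule: agreement on all k domains.* The probability is ∫ Φ((Φ⁻¹(p) + √ρ·z) / √(1−ρ))^k φ(z) dz.

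| p | Three domains, ρ = 0.3 / 0.5 / 0.7 | Seven domains, ρ = 0.3 / 0.5 / 0.7 |
|---|---|---|
| 80% | 57.0 / 61.1 / 65.9% | 35.7 / 44.9 / 54.6% |
| 85% | 65.9 / 69.2 / 73.1% | 45.8 / 54.2 / 62.9% |
| 90% | 75.8 / 78.2 / 81.0% | 58.6 / 65.5 / 72.6% |
| 95% | 87.0 / 88.2 / 89.7% | 75.5 / 79.7 / 84.1% |

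Reading the band edges as 50% and 75%, the grade differs between three and seven domains in six of the nine combinations for p = 80 to 90%, and in none at 95%. This is a property of the rule: requiring agreement on more items always lowers the percentage.

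*Ordinary rule: mean score of at least 4.* Simulated, with assumed shares for scores 1 to 5 of 2/5/13/45/35% (p = 80%), 2/4/9/45/40% (p = 85%) and 1/2/7/45/45% (p = 90%), over the same ρ values.

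| p | Three domains | Seven domains | Gap across ρ |
|---|---|---|---|
| 80% | 68.7–68.9% | 63.9–64.3% | 4.7–5.0 points |
| 85% | 75.3–75.6% | 70.7–72.1% | 3.6–4.8 points |
| 90% | 82.7–84.1% | 78.4–82.1% | 2.0–4.3 points |

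The band is unchanged at 80% and 90%. At 85% the three-domain value lies on the edge of the top band, where sampling error alone could decide the grade.

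*Stricter cut-off, three domains only.* A mean of at least 4.5 at p = 85% gives 34 to 39%, which is in the lowest band.

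**Training.** The target attaches to completion. The Table 1 row on participation carries no threshold of its own. Both can be reported from the attendance log as written.

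**The case for a change.** The strongest opposing argument does not need the domain mismatch. Keep the three domains of Table 1 and vary only the cut-off: at p = 85% the percentage goes from about 75% (mean of at least 4) to 34 to 39% (mean of at least 4.5), from the edge of the top band to the lowest. The bands are the main quantitative yardstick of this pilot. Item wording may sit in a questionnaire or the protocol, but the step from scores to a graded percentage is an analysis definition.

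Part of this stands. The SAP does not define high satisfaction, and the cut-off matters more than the number of domains. But the absence of a rule is not a wrong rule: nothing written in the SAP produces an incorrect percentage. Survey scoring is also commonly kept with the instrument, which is not at hand. The usual choices are familiar: reverse the burden item, count agreement or better as favourable, and show each domain beside the summary. Showing the domains would make an eccentric cut-off visible. Any one rule, including a mean score, is open to debate, since a mean lets a good domain offset a poor one.

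The consequence is limited as well. The grade is descriptive, other percentages are graded too, and interviews with patients, providers and peers inform the same decision. The SAP does not say that this row decides alone.

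**Conclusion.** No change to the plan follows. The apparent clash between three and seven domains is an ambiguity about who answers the longer scale, and a consistent reading is available. The undefined cut-off is a gap that analysts fill sensibly in a descriptive feasibility study.

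Under an ordinary mean-score rule the domain set moves the result by 2.0 to 5.0 points against a sampling half-width of 4.9 points. The larger shifts, such as 65.9% against 45.8% at p = 85% and ρ = 0.3, come from an all-domains rule that the SAP does not state. These sizes rest on assumed agreement rates, correlations, score shares and scale length. They show that bands can shift, not that they will. The half-width takes all 300 respondents as eligible for the row and would be wider with fewer.

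The training wording can be followed as written. The whole-percent bands and the unlisted graded rows are matters of wording only.

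### Patient acceptability is graded as one percentage across provider counselling and peer sessions, so a green light can hide a component in the failure band

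*SAP*

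**What the plan says.** In the SAP, Table 1, under Implementation, the patient acceptability outcome is "Acceptability: % CGW who receive provider counseling or peer session and report high satisfaction". It is one row and one percentage, with the two components joined by an *or*.

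The benchmark paragraph below Table 1 opens "For percentage outcomes we will use the following" and covers feasibility and acceptability in Aim 2, so it applies to this row. The bands are "0-50%: failure of the current intervention design", "51-75%: major revisions required" and "76%: no or minor revisions needed for a confirmatory trial". I call them red, amber and green, and read the last as 76% or more.

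The Questionnaires paragraph gives the purpose of the survey as "to assess acceptability of the provider and peer components of the intervention" (among other things), and adds: "We anticipate that approximately 300 CGW will complete the survey". Under Reach, Table 1 has one row for provider counselling and another for the peer navigator discussion. The analysis text promises a descriptive summary of the Table 1 outcomes. After the qualitative methods, the SAP states: "These qualitative and quantitative data will then be triangulated to refine the interventions for the future full-scale trial".

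The SAP gives no acceptability percentage by component, no band by component, and no rule for women who received both.

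**The concern.** The intervention has two parts that patients meet separately, and a woman may receive one or both. A single percentage over both is a weighted average in which the more commonly received part dominates. The traffic light grades that average.

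What is at stake is the use of the result. The SAP wants the pilot to show how much revision is needed before a confirmatory trial. If one part is well liked and common, and the other poorly liked and less common, the graded figure can fall in the band for little or no revision while the weaker part, taken alone, would be in the failure band. The numerical rule would then give no signal about which part to work on.

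**Working it through.** The SAP states no sample size or precision for this outcome, so there is no figure of its own to reproduce. The check is whether masking can occur, and over what range.

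**Inputs from the SAP**
- Failure band: up to 50%. Green: 76% or more.
- About 300 survey responders.

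**Assumptions (not in the SAP)**
- Provider satisfaction *p₁*: 85% to 95%.
- Peer satisfaction *p₂*: 50%, the top of the failure band.
- Peer share of responses *w*: 10% to 50%.
- All 300 responders received a component, and each contributes one rating to one component.

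**Step 1. Pooled figure.** Pooled = (1 − w)·p₁ + w·p₂. With p₁ = 90% and p₂ = 50%:

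| Peer share | Provider n | Peer n | Satisfied | Pooled | Light |
|---|---|---|---|---|---|
| 10% | 270 | 30 | 243 + 15 = 258 | 86% | green |
| 20% | 240 | 60 | 216 + 30 = 246 | 82% | green |
| 30% | 210 | 90 | 189 + 45 = 234 | 78% | green |
| 40% | 180 | 120 | 162 + 60 = 222 | 74% | amber |
| 50% | 150 | 150 | 135 + 75 = 210 | 70% | amber |

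**Step 2. Largest peer share that stays hidden.** Setting the pooled figure to 0.76 gives w_max = (p₁ − 0.76)/(p₁ − p₂). With p₂ = 0.50:
- p₁ = 0.85: 0.09/0.35 = 25.7%
- p₁ = 0.90: 0.14/0.40 = 35.0%
- p₁ = 0.95: 0.19/0.45 = 42.2%
- p₁ = 1.00: 0.24/0.50 = 48.0%

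So a component at 50% that supplies more than 48% of responses cannot be hidden under green. With peer satisfaction at 40%, the limits fall to 20.0% (p₁ = 0.85: 0.09/0.45) and 34.5% (p₁ = 0.95: 0.19/0.55). The formula is symmetric: if peer sessions were the larger part, they could hide weak provider counselling.

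**Step 3. Is the green light a matter of chance?** Take the 20% case. At a true pooled rate of 82%, treated as one binomial rate, the probability of 228 or more satisfied out of 300 is about 0.996. With the row split, the probability that 60 peer responders with a true rate of 50% reach green (46 or more of 60) is about 0.00002.

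**Step 4. Women who received both.** The SAP does not say how they count. If satisfaction with either part were enough, and the two ratings were independent at 55% and 50%, the figure would be 1 − 0.45 × 0.50 = 77.5%, green with neither part green. This only shows that the missing rule matters; the SAP does not adopt it.

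**Step 5. Precision after a split.** The 95% half-width at a proportion of 50% is 1.96·√(0.25/n): 12.7 points at n = 60, 8.0 at n = 150 and 5.7 at n = 300.

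**The case against.** The strongest defence is that the bands grade the intervention design as a whole, and one overall acceptability figure suits a two-part package. The *or* may only mark who is surveyed and when, since the timing cell refers to a clinical visit or a peer session. A weak part could also surface elsewhere: Reach is shown for each component, twenty patient interviews are planned with attention to type of engagement, and the plan combines qualitative and quantitative results before refining anything. The light is therefore not the only basis for revision.

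Much of this stands, and it lowers the stakes. It does not remove the point. Even if the *or* only defines eligibility, the result is one mixed percentage with one light. Reach shows how many women were touched by each part, not whether they liked it. The interviews carry no benchmark.

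Two stronger readings are tempting and should be resisted:
- A reader might infer that the pilot exists to decide which component to keep, revise or drop. The SAP does not say so; it speaks of refining the interventions for the full-scale trial.
- A reader might infer that both components must be green before going on. Nothing in the SAP asks for this, and it would be a stricter rule. With 240 and 60 independent responders and true satisfaction of 80% in both, the chance that both reach 76% is about 0.74, against 0.96 for the pooled figure. At 78% it is 0.51 against 0.82.

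**Conclusion.** The point holds as a possibility that the graded outcome leaves open, not as a prediction. Under assumed provider satisfaction of 85% to 95% and peer satisfaction of 50%, a green pooled figure hides a failing peer component when peer sessions supply up to about 26% to 42% of responses. It does not at an equal split. Because the SAP gives neither the mix of responders nor expected satisfaction, one cannot say that masking is likely.

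A reader might also infer an effect on error rates or on an efficacy claim. There is none, since this is a descriptive pilot that disclaims effectiveness testing. The consequence is confined to the revise-or-proceed judgement, where the interviews and the planned triangulation offer partial protection. It is a modest improvement, worth making because the outcome is one that the SAP itself grades.

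**What to change.** Replace the single acceptability row in Table 1 with three lines:
1. Percentage highly satisfied among women who received provider counselling, with its band.
2. Percentage highly satisfied among women who completed a peer session, with its band.
3. The pooled figure, with its band, as an overall summary.

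Count a woman who received both in lines 1 and 2, each by her rating of that component, and state how she enters line 3. Show an interval with each percentage. State that the component bands are used to decide which component needs revision before the full-scale trial. The overall go decision need not require both to be green.

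**Cost.** Two further table rows and a sentence on counting. Intervals by component are wider: about ±12.7 points at n = 60 for a proportion of 50%, against ±5.7 for all 300. The survey items must be asked by component, or be linkable to the component received. The stated survey purpose and the timing of the survey suggest that this is feasible, but the items are not shown, so it should be confirmed before the survey is fielded.
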